9. Data Analysis & Statistical Considerations: The primary outcomes of this study are the change in $VO_{2\max}$ and lactate between the “anemic” $VO_{2\max}$ and after transfusion of 2 units of either standard PRBCs or rej-PRBCs “post-Tx” $VO_{2\max}$. We hypothesize that transfusion of RBCs is less effective at increasing oxygen delivery (measured by $VO_{2\max}$ and lactate) compared with transfusion of rej-PRBCs. We expect the changes to be normally distributed and will compare the treatment groups with a 2-group t-test or a rank-sum test if the distribution is non-normal. We will test at a 2-sided significance level of 0.05. The primary analysis will be on an intent-to-treat basis, with follow-up as-treated analysis if necessary. Subjects who withdraw or are excluded before randomization (Day 14) will simply be dropped from analysis. We will further examine the treatment effect in a multivariable regression adjusting for potential effects of baseline $VO_{2\max}$, lactate, hemoglobin, and BMI.

Secondary outcomes include the change in “post-Tx” $VO_{2\max}$ from baseline and differences in these changes will be compared between groups with t-tests or rank-sum tests. Of note, in contrast to the primary endpoint, this secondary analysis may show larger increases in $VO_{2\max}$ attributable to hypervolemia after transfusion. Duration of exercise and peak lactate “post-Tx” will also be compared between study groups.

Based on preliminary data ([name], personal communication), we know that 2 units of autologous, stored PRBCs increase $VO_{2\max}$ on the day of transfusion by $2.4 \pm 0.6 \text{ ml/kg/min}$. Assuming that rej-PRBCs exceed the oxygen delivery of native fresh blood (due to their $p50$ of 40 mmHg compared to 18 mmHg for stored PRBCs and 28 mmHg for normal blood), we anticipate that:

- Pre-transfusion/“anemic” $VO_{2\max}$ will be decreased by 4.6 ml/kg/min from baseline by day 14.
- 2 units rej-RBC will increase $VO_{2\max}$ by $> 6 \text{ ml/kg/min}$ from “anemic” $VO_{2\max}$.
- 2 units control PRBC will only increase $VO_{2\max}$ by 2.5 ml/kg/min from “anemic” $VO_{2\max}$.
- Therefore we will set our expected, measured difference (δ) at 3.5 ml/kg/min .

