Preliminary data also show that the variability of $VO_{2\max}$ has a narrow range, with standard deviation ranging from $0.8-1.9$ for a given subject ([name], personal communication). Combining with our preliminary data (which showed an increase after transfusion of $2.4 \pm 0.6 \text{ ml/kg/min}$ – see above), we set our standard deviation for the power analysis (σ) at $\pm 1.5 \text{ mL/kg/min}$.

Using this data, we can expect 80% power to detect a significant ($p < 0.05$) intergroup difference in the change in $VO_{2\max}$ from anemic to post-transfusion state with 3 volunteers in each group. More patients will be studied as unexpected variability may occur.

10. Data & Safety Monitoring: We will record and analyze both expected and unexpected adverse events in order to monitor for and minimize potential risks to

RESEARCH Summary

Pro00078468

NCT03089047

PI: [name]

human subjects. Adverse events that occur during any study procedure will be collected and reported to the IRB, and FDA as appropriate. The Principal Investigator will review serious and non-serious AEs on a rolling basis as well as in aggregate on a monthly basis. Given the long standing safety of VO₂ max testing as well as blood collection and transfusion studies (many removing far larger volumes of RBCs) we do not expect to see a significant number of adverse events.

11. Privacy, Data Storage & Confidentiality: Study records that identify the patient will be kept confidential as required by law. They will be kept in a locked file cabinet in either the Study Coordinator's or [name] office. Data will also be stored in password protected computers. Except when required by law, the subject will not be identified by name, social security number, address, telephone number, or any other direct personal identifier in study records disclosed outside of Duke University Health System (DUHS). The results of this research study may also be presented at meetings or in publications; however, identity will never be disclosed in those presentations. In no way will any subjects' name be used in any published form.

As part of the study, [name] and the study team will report the results of the study-related laboratory tests named below. These test results will be recorded in the study record and results of tests and studies done solely for this research study will not be included in the volunteer's medical record.

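### The power SD of 1.5 is not derived on the scale of the change in VO2max and sits in the optimistic part of the converted range; the planned t-test has 58%, not 80%, power with 3 per group

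*Combined protocol and SAP*

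**What the plan says.** All of the following is in section 9 of the combined protocol and SAP unless another section is named.

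- **Endpoint.** The primary VO2max outcome is the change from the anemic test to the post-transfusion test. The power statement concerns the "intergroup difference in the change in" VO2max.
- **Test.** The analysts "will compare the treatment groups with a 2-group t-test or a rank-sum test if the distribution is non-normal", and "We will test at a 2-sided significance level of 0.05".
- **Effect.** "Therefore we will set our expected, measured difference (δ) at" 3.5 ml/kg/min, the gap between an expected gain of more than 6 with rejuvenated cells and 2.5 with control cells.
- **SD.** VO2max for a given subject "has a narrow range, with standard deviation ranging from" 0.8 to 1.9. This is combined with the preliminary increase of 2.4 ± 0.6 ml/kg/min, and then "we set our standard deviation for the power analysis (σ) at" 1.5.
- **Claim.** "we can expect 80% power to detect a significant" difference with 3 volunteers in each group. The section adds that more will be studied in case variability is greater than expected, without giving a number.
- **Size.** Section 4 plans 20 enrolled under Study size. Inclusion criterion iii says 20 are screened to obtain 10 who donate.

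**The concern.** The SD in a two-group comparison of changes must be the between-subject SD of the change. One source for the 1.5 describes repeated VO2max values in one person, most naturally the SD of a single test. The other describes a change, but its ± could be an SD or a standard error. The plan gives no formula for combining them and no step from one test to a difference of two, so a reader cannot reconstruct 1.5 or judge whether it is cautious.

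The 80% figure is the only statement of power in the plan. If the SD is optimistic, or if the calculation does not match the planned test, a non-significant result from this small pilot could be read as stronger evidence against an effect than it is.

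**Working it through.** **Inputs.** From section 9: difference 3.5, SD 1.5, two-sided alpha 0.05, two-group t-test, 3 per group, single-subject SD 0.8-1.9, change 2.4 ± 0.6. The plan gives no unit for 0.8-1.9; mL/kg/min is assumed. That range is read as a single-test SD.

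**1. Reproduce the stated figure.** Normal approximation, with 1.5 taken as the SD of the change:
- n per group = 2 × [1.5 × (1.960 + 0.842) / 3.5]² = 2.88, rounded up to 3.
- Standard error = 1.5 × √(2/3) = 1.225, and 3.5 / 1.225 = 2.858.
- Power = Φ(2.858 − 1.960) = 81.5%.

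The 80% claim therefore reproduces by this method.

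**2. Use the planned test, with the SD unchanged.** With 3 per group the t-test has 4 degrees of freedom and a critical value of 2.776 instead of 1.960. The noncentral t with noncentrality 2.858 gives 58.0% power. At SD 1.5, power is 78.4% with 4 per group and 89.6% with 5. This shortfall comes from the normal approximation and has nothing to do with the scale of the SD. The rank-sum fallback is no help at 3 per group: its smallest exact two-sided p-value is 2/20 = 0.10.

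**3. Put the repeatability range on the change scale.** In general, SD(change) = s × √[2(1 − ρ)], where s is the single-test SD and ρ the correlation between the two test errors; variation in response between subjects would add to this. With ρ = 0 and no such variation:
- √2 × 0.8 = 1.13
- √2 × 1.35 (midpoint of 0.8 and 1.9) = 1.91
- √2 × 1.9 = 2.69

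Working back, 1.5 / √2 = 1.06, so the chosen SD corresponds to a single-test SD below the midpoint of 1.35.

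**4. Power of the two-sided t-test for a difference of 3.5.**

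| Per arm | Change SD 1.13 | 1.5 | 1.91 | 2.69 |
|---|---|---|---|---|
| 3 | 80.5% | 58.0% | 40.4% | 23.5% |
| 5 | 98.9% | 89.6% | 71.9% | 44.1% |
| 10 | >99% | 99.8% | 97.2% | 78.7% |

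The 5 and 10 per arm correspond to 10 donors and 20 enrolled, split equally.

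**5. Largest change SD that still gives 80% t-test power.** It is 1.14 at 3 per arm, essentially the bottom of the converted range; 1.73 at 5 per arm (single-test SD 1.22); and 2.64 at 10 per arm. At 2.69, 80% needs 11 per arm.

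**6. Compare the two sources.** If 0.6 is the SD of the change and errors are independent, the single-test SD is at most 0.6 / √2 = 0.42, below the plan's minimum of 0.8. If 0.6 is a standard error, the SD depends on a sample size that is not reported.

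**The case against.** The best defence is that 1.5 is a reasonable working value. It lies inside 1.13-2.69 and is 2.5 times the only spread quoted for the change itself. A reader might infer that the plan's repeatability data contradict 1.5; they do not. This part of the defence stands.

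Nor is √2 a lower bound. Both tests take place on the same day, and the plan aims to have the same two facilitators present. If 0.8-1.9 includes day-to-day variation, which the plan does not say, the shared part cancels in the difference. A change SD of 1.5 follows from s = 1.35 with ρ = 0.38, or from s = 1.9 with ρ = 0.69. Likewise, 0.6 as an SD of change fits s = 0.8 if ρ = 0.72. A reader might therefore conclude that 0.6 must be a standard error, but the documents do not settle it. Varying response to transfusion would push the change SD up, so the net direction is unknown.

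The range may also describe individual subjects' SDs. In that case 2.69 treats everyone as being as variable as the most variable subject, and a pooled value would be lower.

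Finally, this is a pilot that expects to exceed 3 per group, which limits the practical consequence. It does not supply the missing derivation or correct the 80% claim, and the number to be randomised is not clear from section 4.

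**Conclusion.** The point holds in a limited form. Sigma = 1.5 is underived, is not shown to be on the scale of the endpoint, and lies in the optimistic part of the range obtained under independent errors and constant response. The statement of 80% power with 3 per group is not delivered by the planned t-test: it gives 58% at the plan's own SD, and reaches 80% only if the change SD is about 1.14 or less. These are two separate defects, and the fall from 80% to 58% belongs to the second alone.

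A reader might go further and infer that a null result is likely even if the full 3.5 effect exists. The documents do not support that at the sizes the plan aims for. At 10 per arm, power is about 79% even at the top of the range. At 5 per arm it is 72% at the midpoint, and falls below one half only near the top, at a single-test SD above about 1.76. Power at 5 per arm does fall below 80% once the single-test SD exceeds 1.22, so the claim is not secure across the plan's own figures at that size either.

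The size of the effect depends on reading 0.8-1.9 as a single-test SD in mL/kg/min, on equal allocation, and on the correlation and response assumptions stated above.

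**What to change.** Rewrite the power paragraph in section 9:

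1. State whether the 0.6 is an SD or a standard error and, if the latter, the number of subjects behind it.
2. Define sigma as the SD of the anemic to post-transfusion change. Show how it follows from the preliminary data, including the assumed correlation between the two same-day tests and any allowance for varying response.
3. Replace the claim of 80% with 3 per group by t-based power over a plausible range of change SDs, at the number actually to be randomised. Under independence, that range is 1.13-2.69.

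This is a change of wording. It needs no new data and no change in enrolment. The cost is that the stated power becomes less favourable.

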previous experience, we anticipate that up to 25% of the subjects will fall into this category; therefore, 20 subjects will be screened to obtain 10 participants who go on to donate their blood.

- iv. Calculated total blood volume of at least 4,500 mL using an established formula:

- a. Men: $(0.006012 \times H^3) + (14.6 \times W) + 604 = TBV$
- b. Women: $(0.005835 \times H^3) + (15 \times W) + 183 = TBV$

[H= Height in inches; W=Weight in pounds]

- v. Has access to transportation to visit the blood collection facility and to return to Duke for all study visits
- vi. Weighs at least 130 pounds

Exclusion Criteria:

- i. Any significant acute or chronic medical illness or problem, including, but not limited to, diabetes, hypertension, cardiac disease, asthma, COPD
- ii. Current or recent (last 60 days) tobacco or nicotine use
- iii. History of sickle cell trait or disease or any other acquired or hereditary hematological abnormality
- iv. History of fainting or other significant adverse reaction during phlebotomy or donation of blood
- v. Known prolonged QTc (or evidence of such at screening) defined as QTc >470 ms
- vi. Known or suspected illicit drug or alcohol abuse
- vii. Known or suspected HIV, Hepatitis B, or Hepatitis C infection
- viii. History of thrombophilia or anticoagulant therapy
- ix. Pregnancy
- x. Obesity defined as BMI>30
- xi. Recent history of blood donation:
 - a. Single whole blood unit donation within the past 8 weeks
 - b. Double RBC donation by apheresis within the past 16 weeks
 - c. Plasma donation by apheresis within the past 4 weeks
 - d. Any self-reported blood donation within a year
- xii. Inadequate red blood cell mass evidenced by total blood volume <4500 mL (above) or screening hemoglobin <13.3 g/dL
- xiii. Known hypersensitivity to lithium compounds. And known taking lithium salts for treatment of other medical/psychiatric conditions

RESEARCH Summary

Pro00078468

NCT03089047

PI: [name]

xiv. Students and employees who are under direct supervision of the investigators

Study structure: study visits (A-E).

A	Screen	Screen, consent, H&P, ECG, screening labs, and VO ₂ max
B	Day 0	Donate 2 units of PRBCs by autologous apheresis
C	Day 14	8am Measure pre-transfusion, “anemic” VO ₂ max 9 am Transfuse 2 units of standard or rejuvenated PRBCs 3 pm Measure post-transfusion VO ₂ max (end of study)

listed in this study.

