Small amount of blood [3 lavender topped tubes] will be collected from subject to test for hemoglobin, type & screen and 1 cross match to verify the donated blood received from

RESEARCH Summary

Pro00078468

NCT03089047

PI: [name]

The Blood Connection belongs to the same subject who arrives at the appointed date at Duke facility

Anemic VO₂max

Three minutes of resting baseline measures will be recorded before the start of exercise. The subject will then begin to pedal the cycle ergometer at a cadence of 75 rpm. Resistance will be manually set according to a standardized, progressive protocol. A rating of perceived exertion (RPE) will be obtained at the end of each exercise stage. Vital signs will be recorded every 3 minutes, and ECG monitoring will be continuous. Exercise will be terminated when the subject reaches volitional fatigue. VO₂max will be reported as the highest oxygen consumption averaged over two 30-second periods, which typically occurs in the last stage of the progressive maximal exercise test. Maximum heart rate will be the heart rate at or near VO₂max. To minimize variability in VO₂max testing procedures, the same 2 facilitators (an engineer/technician and a research staff) will be present at every test. Radial arterial access will be obtained for cardiac output monitoring (LiDCO pulse contour analysis) at this visit.

Tx and post-Tx VO₂max

Duke Transfusion Services will randomize each subject to receive 2 units of standard PRBCs or rejRBCs over 120 minutes using a standard infusion pump. All units will be washed to equalize the transfusion volumes; rejuvenation includes a mandatory washing step. Rejuvenation of donated blood will be done according to the procedures in the labeling of the Rejuvesol product. Vital signs will be monitored and recorded every 15 minutes. After a total 4-hour rest after completing the first VO₂max testing, and a light snack, the exercise test will be repeated.

Laboratory testing: The p50 will be measured in one of the blood units transfused and in the subject before the exercise test. Radial arterial access will be obtained for serial cardiac output monitoring (LiDCO Pulse Contour Analysis, LiDCO Products, London, UK), arterial blood gas analysis and lactate measurement before and after transfusion, and after exercise testing. Final blood collected for a hemoglobin level will be done at the conclusion of blood transfusion. This is the final visit and participation is completed.

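### The stated 80% power with 3 volunteers per group is 58% for the planned t-test; 5 per group is the smallest equal size that reaches 80%

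*Combined protocol and SAP*

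**What the plan says.** Section 9 (Data Analysis & Statistical Considerations) makes the change in VO₂max from the anemic test to the post-transfusion test a primary outcome, together with lactate. The analysis will "compare the treatment groups with a 2-group t-test or a rank-sum test if the distribution is non-normal", and "We will test at a 2-sided significance level of 0.05". The expected difference is set at 3.5 mL/kg/min.

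For the SD, Section 9 cites preliminary data in which VO₂max "has a narrow range, with standard deviation ranging from" 0.8 to 1.9 for a given subject. It combines these with an observed rise of 2.4 ± 0.6 after transfusion and settles on 1.5 mL/kg/min.

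The power statement follows: "Using this data, we can expect 80% power to detect a significant" difference between groups in the change "from anemic to post-transfusion state with 3 volunteers in each group. More patients will be studied as unexpected variability may occur". This is the only power figure in the document.

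On numbers, Section 4 (Study size) plans to enroll 20 subjects, and inclusion criterion iii explains that "therefore, 20 subjects will be screened to obtain 10 participants who go on to donate their blood". Randomisation comes later, at the Day 14 visit: "Duke Transfusion Services will randomize each subject to receive 2 units of standard PRBCs or rejRBCs". Section 9 adds that "Subjects who withdraw or are excluded before randomization (Day 14) will simply be dropped from analysis". Neither the number to be randomised nor the allocation ratio is given.

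**The concern.** Three per group leaves a two-sample t-test with 4 degrees of freedom. The two-sided critical value is then 2.776 rather than 1.960, so a sample size that just reaches 80% on the normal scale must fall well short with the t-test. The rank-sum fallback is worse: with three against three, an exact test cannot give a two-sided p below 0.05 whatever the data.

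The figure matters because it tells the investigators how many losses the study can absorb. Read at face value, 6 randomised volunteers are enough, and 10 donors could lose 4 before Day 14. The plan foresees such losses: Section 6 allows exclusion for fever after donation, and Section 7 sets payment for donors who miss later visits. Section 9 also presents volunteers beyond 6 as protection against unexpected variability. If the t-test governs, some of them are needed to reach 80% even when variability is exactly as assumed.

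**Working it through.** **Inputs (all from Section 9).** Difference δ = 3.5; SD σ = 1.5; two-sided α = 0.05; target power 80%; two-group t-test. Standardised difference d = 3.5/1.5 = 2.333.

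**Step 1: reproduce the stated figure.** The normal approximation gives n per group = 2(1.960 + 0.8416)²/d² = 2 × 7.849/5.444 = 2.88, rounded up to 3. Power at n = 3 is Φ(2.858 − 1.960) = 81.5%. This is the likely source of the 80%; the plan does not name its formula.

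**Step 2: power of the planned test.** For the pooled t-test, power comes from the noncentral t distribution with n₁ + n₂ − 2 degrees of freedom and noncentrality δ/(σ√(1/n₁ + 1/n₂)). At 3 v 3 the noncentrality is 3.5/(1.5 × 0.8165) = 2.858.

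| Groups | df | Noncentrality | Critical t | Power |
|---|---|---|---|---|
| 3 v 3 | 4 | 2.858 | 2.776 | 58.0% |
| 4 v 4 | 6 | 3.300 | 2.447 | 78.4% |
| 5 v 4 | 7 | 3.478 | 2.365 | 84.5% |
| 5 v 5 | 8 | 3.689 | 2.306 | 89.6% |

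Simulation with 200,000 trials per size agrees: 58.2% at 3 v 3, 78.4% at 4 v 4 and 89.5% at 5 v 5. A one-sided t-test at 3 v 3 would still reach only 75.7%. For 80% at 3 per group the SD would have to be at most 1.14, or the difference about 4.6.

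**Step 3: rank-sum fallback.** There are 20 ways to split six values three and three, so the smallest exact two-sided p is 2/20 = 0.10. With complete separation the continuity-corrected p is 0.081, and only the uncorrected asymptotic version passes, at 0.0495. The plan does not say which version it means. Simulated exact power with normal data is 0% at 3 v 3, 62% at 4 v 4, 73% at 5 v 4 and 81% at 5 v 5.

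**Step 4: margin from 10 donors, allocated as evenly as possible.** Losing one leaves 5 v 4, at 84.5%. Losing two leaves 4 v 4, at 78.4%, and no other split of 8 does better. The tolerable loss is therefore one, not four.

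**Step 5: sensitivity to the SD.** The endpoint is a within-subject change, but the 0.8 to 1.9 range describes single tests. If the errors of the two tests were independent, the SD of the change would be √2 × 0.8 = 1.13 to √2 × 1.9 = 2.69. Independence is an assumption. Both tests are on the same day, and positive correlation would lower these values.

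| SD of change | 3 per group | 5 per group |
|---|---|---|
| 1.13 | 81% | 99% |
| 1.5 | 58% | 90% |
| 1.9 | 41% | 72% |
| 2.69 | 23% | 44% |

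At 5 per group, 80% power holds up to an SD of 1.73.

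**The case against.** The strongest reply is that 3 per group is not the planned size. The plan says that more will be studied, Section 4 expects 10 donors, and the Study size paragraph speaks of 20 enrolled. If up to 25% of 20 failed the VO₂max screen, 15 would remain, and 8 v 7 has 98.6% power. No passage plans to stop at 6. The stated figure also follows from a recognised formula, so the fault lies in the choice of method rather than in the sums. This is correct, and it is why the point does not amount to a claim that the trial is underpowered. But the sentence promising more volunteers gives no number. Criterion iii describes the 20 as screened to yield 10 donors, and the only power figure offered is still wrong for the test that will be used.

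A second reply is that the inputs are cautious. If the ± 0.6 attached to the observed rise is an SD of the change, 3 v 3 has over 99% power, and the difference of 3.5 rests on a rise of more than 6 with rejuvenated cells. The plan does not say whether ± 0.6 is an SD, and it chose 1.5 for its own calculation. The power statement has to be true at that value.

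Third, the context implies that σ is the SD of the change, and the rank-sum test is only a fallback. Both are fair. Clarifying them is useful, but the main correction does not depend on it.

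**Conclusion.** The concern holds. At the plan's own difference, SD and significance level, the planned t-test has 58% power with 3 per group, 22 points below the stated 80%. The smallest equal group size that reaches 80% is 5. This rests on normally distributed changes with a common SD of 1.5.

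The consequence is limited but real. Ten volunteers randomised equally would give about 90% power, so the design may well be adequate. However, the number randomised and the ratio are unstated, and the tolerance for losses is much smaller than the stated figure suggests. The statement should be corrected. The result at 3 per group is certain; the margin argument depends on taking 10 donors as the working number.

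**What to change.** Replace the 3-per-group sentence with t-based power at the number intended to be randomised. If that is 10, allocated 1:1, wording could be:

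> With 5 volunteers per group, a two-sided t-test at the 0.05 level has about 90% power for a difference of 3.5 mL/kg/min if the SD of the within-subject change is 1.5. Power is 99% if the SD is 1.13, 72% if it is 1.9 and 44% if it is 2.69.

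If losses between donation and Day 14 are expected, add 85% for 5 v 4 and 78% for 4 v 4. State the target number randomised and the allocation ratio in advance, independently of outcome data. Say that σ is the SD of the within-subject change, and that any rank-sum test will be exact.

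The cost is protocol wording only. No extra participants are needed if about 10 are randomised equally, which is an assumption because the plan gives 10 as the number of donors. The stated power at 3 per group becomes less favourable.

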- 3) Decreased hemoglobin level: Volunteers should not exhibit significant anemia during the study since a hemoglobin of at least 12.5 g/dL is required at The Blood Connection prior to donation of blood. Based on previous studies we expect the lowest hemoglobin levels to be approximately 11-12 g/dL (hematocrit of 33-36%) after donation. Volunteers will be told that while anemia of this level is not dangerous, they may feel fatigued and have decreased exercise performance until their hemoglobin level is increased on Day 14(Study visit C).
- 4) Risks of blood transfusion:
 - a. During blood donation bacteria may be introduced into the donated unit because it is impossible to completely sterilize the skin through which venipuncture occurs. Also, donors may have asymptomatic infection of bacteria in the blood stream due to recent dental procedures or developing illness. The reported rates for allogeneic RBC unit bacterial contamination range from 0.01% to 0.27%. As the subjects in this study have allogeneic donor criteria applied to them, this would be a fair

RESEARCH Summary

Pro00078468

NCT03089047

PI: [name]

estimation of bacterial contamination risk. If the subject experiences fever within 2 days after donating their unit of whole blood, they will be asked to call [name]. The subject may be excluded from continued participation in the study

- b. Additional transfusion reactions, such as chills, fever, drop in blood pressure, shortness of breath, and (very rarely) shock may also occur. There may also be allergic reactions such as hives, rashes, or (very rarely) anaphylactic reactions that could result in death.
- c. The subject may experience pain around the IV site or in this arm with the IV. Investigators will select the largest available vein in the forearm or antecubital fossa to minimize pain during blood infusion.
- d. Mistransfusion, arising from errors in unit labeling, component preparation or other clerical errors occurs in 1:16,000 - 1:25,000 autologous donations. To minimize the risk of mistransfusion, which in the worst possible case may trigger a fatal or serious acute reaction, multiple safeguards to prevent this are written into our study protocol and include the following:
 - i) multiple sample and bag identification checks
 - ii) 2 persons will confirm the subject's identity with the stored RBCs, using standard Duke Medical Center transfusion procedures

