 - iii) an extended crossmatch will be performed between the subject's stored donated unit and a fresh sample of the subject's blood
 - iv) only one subject per day will be transfused to minimize risks
 - v) the research subject will be asked to review the autologous RBC unit label including their own name, and date of birth to confirm they are receiving their own blood
- e. **Additional risk of rejuvenated blood: If lung function is abnormal, use of rejuvenated blood may lower the subject's oxygen levels making him/her short of breath.**

5) Risks associated with exercise testing: The most common complaint from those performing the exercise test on a bicycle is thigh pain during the test. In healthy volunteers, the likelihood of death or a serious complication, e.g. sustained arrhythmia, is low, but not impossible. The following is language from a recent publication: *Risks of Physical Activity, Exercise Training, and Exercise Testing. Recommendation 1: Maximal exercise stress testing is associated with a very low risk of fatal and non-fatal cardiac events in either healthy asymptomatic or clinical populations. In healthy, asymptomatic individuals, the respective incidences of fatal and nonfatal events are approximately 0.3-0.8/10,000 tests and 1.4/10,000 tests (Level 3, Grade B).*¹⁴

6) Risks associated with arterial catheter placement: Arterial catheter insertion in the wrist can cause occlusion of the radial artery, although most instances occur after many hours or days of a catheter in place. Radial artery catheterization has been used extensively in our laboratory, with more than 200 being performed in healthy volunteer studies with no significant complications. The arterial line insertion (standard 20 g) will be performed by an experienced anesthesiologist under sterile technique with local anesthetic.

7) Risks associated with LiDCO cardiac output monitoring:

RESEARCH Summary

Pro00078468

NCT03089047

PI: [name]

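### Adverse event collection is tied to study procedures, with no stated window and no active follow-up between visits or after Day 14, so delayed events that the plan itself names may be missed

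*Combined protocol and SAP*

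**What the plan says.** Section 10 (Data & Safety Monitoring) makes three statements about adverse events. The first is general: "We will record and analyze both expected and unexpected adverse events in order to monitor for and minimize potential risks to" human subjects. The second sets the scope of collection and reporting: "Adverse events that occur during any study procedure will be collected and reported to the IRB, and FDA as appropriate". The third describes oversight: "The Principal Investigator will review serious and non-serious AEs on a rolling basis as well as in aggregate on a monthly basis". None gives a start date, an end date or a method of asking.

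Section 4 lists three visits: screening (A), donation on Day 0 (B), and Day 14 (C), which contains both exercise tests and the transfusion. The table marks the 3 pm test as the end of the study, and the Visit C text closes with "This is the final visit and participation is completed". Visit C describes blood samples, vital signs, ECG monitoring and arterial measurements. It does not describe a question about events since donation.

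Section 6 has one reporting route between visits (item 4a): "If the subject experiences fever within 2 days after donating their unit of whole blood, they will be asked to call" the study team. The stated consequence is possible exclusion from the study.

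**The concern.** The sentence that defines collection follows the procedures, while the risk section describes harms that need not appear during one. A coordinator who applies that sentence literally would have no reason to log thrombophlebitis noticed some days after donation, or a hand problem noticed the day after the arterial catheter was removed.

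What is at stake is the completeness of the safety record in healthy volunteers. The investigator's rolling and monthly reviews can act only on events that reach the study. If nobody asks, a low count of events may reflect the absence of a question rather than the absence of harm.

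**Working it through.** The plan gives no figure to reproduce here, so the check sets passages side by side, with some clock arithmetic.

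**1. Scheduled contact.** Visit B is Day 0 and Visit C is Day 14, so 14 − 0 = 14 days pass without a scheduled contact. Participation ends at Visit C, so there are 0 days of follow-up after it.

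**2. Observation after transfusion.** Inputs from section 4: the first test is at 8 am; the table entry "9 am Transfuse 2 units of standard or rejuvenated PRBCs" sets the start of transfusion; it runs 120 minutes; the second test is at 3 pm. From section 4 and the stage table in section 5: 3 minutes of resting baseline and at most 21 minutes of exercise.

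- On the visit table: 9:00 + 2 h = 11:00, and 15:00 − 11:00 = 4 h. Adding the test (3 + 21 = 24 min) gives at most about 4 h 24 min.
- On the Visit C text, which places the second test after a 4-hour rest from the end of the first: 8:00 + 24 min + 4 h = 12:24, and 12:24 − 11:00 = 1 h 24 min to the start of the second test. This assumes the first test starts at 8 am, runs through every stage, and is followed by a rest of exactly 4 hours.

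The two descriptions of the day need reconciling. On either one, described observation ends within hours of the transfusion.

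**3. Named harms against the stated collection rule.**

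| Harm named in section 6 | When it could be noticed | Stated way of capturing it outside a procedure |
|---|---|---|
| Hematoma, nerve injury, thrombophlebitis (item 1) | After leaving the donation site | None |
| Post-donation fatigue (items 2 and 3) | Days 0 to 14 | None |
| Infection from a contaminated unit (item 4a) | After Visit C | None; the fever call concerns the days after donation |
| Fever after donation (item 4a) | Days 0 to 2 | Subject's own call |
| Radial artery occlusion (item 6) | After catheter removal | None |

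The plan itself places two of these outside a visit: fever within 2 days of donation, and anemia, about which volunteers are told that "they may feel fatigued and have decreased exercise performance until their hemoglobin level is increased on Day 14". It gives no onset times for the others. That they can appear after a subject has gone home is an assumption, though an ordinary one.

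**4. The one reporting route.** The fever call covers one symptom over 2 of the 14 days. The text does not say that the fever is entered as an adverse event.

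**The case against.** The strongest reply is that section 10 opens with an unrestricted promise to record expected and unexpected events, and nothing bars the team from logging one that a subject reports unprompted. That stands. A reader might infer that events outside procedures are excluded and will never be counted; the documents do not support this. They show two adjacent sentences that differ in scope, and no active means of finding the events.

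Some harms are also better covered than a quick reading suggests. Transfusion is itself a study procedure with vital signs every 15 minutes, and section 6 gives no onset time for chills, fever or allergic reactions, so these are not shown to fall outside collection. The anemia is the intended experimental state, and hemoglobin is measured at Visit C. Consent pages and the questionnaires are not available here, so instructions to subjects on reporting cannot be checked.

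Three further inferences should be resisted.

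- A reader might expect the pilot to declare rejuvenated cells well tolerated on thin data. Section 9 plans only physiological and exercise outcomes, and no tolerability conclusion. Events before Day 14 also precede randomization, so they cannot bear on a comparison of the arms.
- A reader might use the contamination rates in item 4a to size the gap. Those give the chance that a unit is contaminated, not that an adverse event occurs or is missed.
- A reader might set the reassurance on radial occlusion, "although most instances occur after many hours or days of a catheter in place", against a catheter kept in for most of Day 14. The plan states no removal time, and it also relies on more than 200 catheterizations in healthy volunteers without significant complications. No contradiction is shown.

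**Conclusion.** The point holds as a gap in active ascertainment. Section 10 states no collection period, and its two sentences on scope do not agree. No adverse event question at Visit C and no contact after Day 14 is described. Delayed events of kinds the plan names may therefore be missed unless a subject reports them unprompted.

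Its size is the 14 days between donation and Visit C, relieved only by the fever call, and all time after Day 14, with roughly 4 hours of observation after transfusion on the visit table. How many events would be lost cannot be calculated from the documents. The conclusion assumes that the collection sentence is applied as written and that no removed page sets a wider rule. It does not touch the primary outcomes, sample size, power or significance level. This is a cheap improvement.

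**What to change.** Replace the collection sentence in section 10 with: *All adverse events from consent (including the Visit A exercise test) to the post-Day-14 contact will be collected, whether or not they occur during a study procedure, and will be reported to the IRB and, where applicable, to the FDA.* Starting at consent keeps events at the screening exercise test in scope, and the last clause keeps the reporting duty. Add where the window closes for someone who leaves before transfusion.

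In Visit C, add a standard question on arrival about events since donation. Add one telephone contact after Day 14, at an interval set by the investigator and the transfusion service. Move the end of participation, in both the visit table and the Visit C text, to that contact.

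The cost is a short amendment, one question at an existing visit and one short call per transfused subject: about 10 on the number of donors expected in the eligibility section, up to 20 if every planned enrollee is transfused. More minor events will be recorded.
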